4.3.2 Primary Efficacy Endpoint

4.3.2.1 Primary analysis

The estimand of the primary analysis is the mean difference of the change from baseline CDR-SB scores at Week 78 between treatment groups in the ITT population [ICH E9 (R1) Addendum 2014, 2017]. All observed data will be included in the primary analysis, including data collected after intercurrent events [ICH E9 (R1) Addendum 2017], i.e., treatment discontinuation or a change in concomitant use of AD symptomatic medication.

The change from baseline CDR-SB scores will be summarized by treatment group at each post-baseline visit. A mixed model repeated measures (MMRM) model will be used as the primary analysis to analyze change from baseline CDR-SB using fixed effects of treatment group, time (categorical), treatment group-by-time interaction, baseline CDR-SB, baseline CDR-SB by time interaction, baseline MMSE, AD symptomatic medication use at baseline (yes/no; see Section 4.2.3 for definition of AD symptomatic medication use at baseline),

Final V1.0

region, and laboratory ApoE £4 status (carrier/non-carrier). An unstructured covariance matrix will be used to model the within-patient variance-covariance errors. If the unstructured covariance structure matrix results in a lack of convergence, the heterogeneous Toeplitz covariance structure followed by the heterogeneous first-order autoregressive covariance structure will be used. The Kenward-Roger approximation will be used to estimate the denominator degrees of freedom. In the primary analysis, missing data are assumed to be missing at random [Rubin 1976].

4.3.2.2 Sensitivity analysis

The following sensitivity analyses will be performed to assess the robustness of the primary analysis to deviation from the missing-at-random assumption. All the sensitivity analyses will be conducted for the ITT population.

4.3.2.2.1 Pattern mixture model

The pattern mixture model (PMM) represents a general and flexible framework to model the predictive distribution of missing data conditional on the observed data [Little 1993, 1994]. It allows formulating assumptions regarding missing data in a transparent and clinically interpretable manner.

In the PMM framework, subjects are grouped into missing patterns so that subjects in the same pattern share similar missingness characteristics. In this analysis, missing patterns will be defined according to the reasons for early withdrawal from study as reported on the electronic case report form (eCRF). The following two patterns will be considered:

- Subjects who withdraw due to reasons that may be related to efficacy, including consent withdrawn, withdrawal by parent/guardian, investigator decision, loss of capacity, change of treatment, and disease progression;
- Subjects who withdraw due to reasons that are unlikely related to efficacy, including adverse event, lost to follow-up, death, pregnancy, relocation, protocol amendment, site terminated by sponsor/investigator, study visit burden, and other.

Subjects who withdraw due to reasons that may be related to efficacy will be penalized and their missing data will be imputed using the copy increment from reference (CIR) method [Carpenter et al. 2013] (see Section 4.3.2.2.2 for description of the CIR method). Subjects who withdraw due to reasons that are unlikely related to efficacy will be handled using the missing-at-random assumption and their missing data will be imputed using the standard multiple imputation method [Rubin 1987]. Subjects with missing data due to reasons other than early withdrawal (such as item missing, out of window, etc.) will be handled using the missing-at-random assumption. For both imputation methods, the following covariates will be included in the imputation model: treatment group, baseline CDR-SB, baseline MMSE, AD symptomatic medication use at baseline (yes/no), region, and laboratory ApoE £4 status (carrier/non-carrier). Implementation details can be found in Appendix 6.3.2.

The imputed datasets will be analyzed by an analysis of covariance (ANCOVA) model adjusting treatment group, baseline CDR-SB, baseline MMSE, AD symptomatic medication use at baseline (yes/no), region, and laboratory ApoE & status (carrier/non-carrier). The analyzed results from the imputed datasets will be combined based on Rubin's rules [Rubin

Final V1.0

1987] assuming that the statistics estimated from each imputed dataset are normally distributed.

If intermediate missing values are encountered (such as data missing at Week 26 but are available at subsequent visits), a Markov chain Monte Carlo (MCMC) method that assumes multivariate normality will be used to impute the intermediate missing values and produce a monotone missing pattern (data with only terminal missing and no intermediate missing) [Li 1988; Schafer 1997].

4.3.2.2.2 Copy increment from reference method

The copy increment from reference (CIR) method will be applied to impute the post-withdrawal data for any aducanumab-treated subject who withdraws from study early based on data from the placebo group rather than the subject's own randomized treatment group [Carpenter et al. 2013]. Specifically, for a subject on aducanumab high dose (or aducanumab low dose) who withdraws early, his or her mean trajectory after early withdrawal is assumed to be parallel to the mean trajectory of the placebo group, and the difference between the two means is the same as the difference at the time of withdrawal. This method assumes that any benefit gained from previous treatment will be retained, but subjects progress as if they were on placebo after withdrawal from study. For any subject on placebo who withdraws early, his or her post-withdrawal profile will be imputed following the missing-at-random principle. Implementation details can be found in Appendix 6.3.1.

After all missing data have been imputed, an ANCOVA model adjusting treatment group, baseline CDR-SB, baseline MMSE, AD symptomatic medication use at baseline (yes/no), region, and laboratory ApoE ε4 status (carrier/non-carrier) will be applied to analyze the change from baseline CDR-SB.

4.3.2.2.3 Imputation by natural disease progression

Subjects are assumed to exhibit an evolution of the disease similar as the natural disease progression after early withdrawal from study (for all treatment groups). The natural disease progression is determined based on a snapshot of the Alzheimer's Disease Neuroimaging Initiative (ADNI) database [Mueller et al. 2005] obtained in May 2017. A subpopulation was defined that satisfies the major inclusion criteria of Study 221AD301 (and the identically designed Study 221AD302). In this subpopulation, the mean change from baseline CDR-SB at Week 78 is estimated to be about 1.52 for subjects with late mild cognitive impairment (LMCI) and about 2.06 for subjects with mild AD. The missing data at Week 78 for this study will be imputed using the linear extrapolation approach based on subjects' baseline clinical stage (MCI due to AD or mild AD). For example, assuming a mild AD patient whose last non-missing change from baseline CDR-SB measurement is 0.5 at Week 26, the change from baseline CDR-SB at Week 78 for this patient will be imputed as 0.5+2.06*(78-26)/78, which is 1.87. A similar algorithm will be applied to the MCI patients. After imputation, the change from baseline CDR-SB at Week 78 will be analyzed by an ANCOVA model adjusting treatment group, baseline CDR-SB, baseline MMSE, AD symptomatic medication use at baseline (yes/no), region, and laboratory ApoE & status (carrier/non-carrier).

4.3.2.2.4 Tipping point analysis

Final V1.0

The tipping-point analysis is a progressive stress-testing to assess how severe departures from missing-at-random must be in order to overturn the conclusion of the primary analysis [Yan et al. 2009]. For our study, subjects are assumed to have worse scores after early withdrawal from study compared to subjects who remain on study.

The missing data are first imputed by the standard multiple imputation (assuming missing at random). To reflect the worse performance after early withdrawal, pre-specified shift parameters δ_c and δ_t are added to the imputed values for subjects on placebo and aducanumab (include both low dose and high dose), respectively. The adjusted multiple imputed datasets will then be analyzed by an ANCOVA model and the results will be combined using the Rubin's rule for inference.

A range of shift parameters δ_c and δ_t will be applied and p-value will be calculated for each combination of δ_c and δ_t . The tipping region is defined as the combinations of δ_c and δ_t such that the treatment effect is no longer significant (p-value greater than the significance level).

The scientific plausibility of the tipping region will be evaluated. If implausible departures from the missing-at-random assumption (large δ) are needed in order to change the results from statistically significant to insignificant, the results of the primary analysis are considered to be robust to departure from the missing-at-random assumption.

4.3.2.3 Supplementary analysis

4.3.2.3.1 Censoring after intercurrent events

The primary analysis (Section 4.3.2.1) will be repeated with the data censored after any of the following intercurrent events (if multiple events occur to the same subject, data after the earliest event will be censored):

- o premature discontinuation of the study treatment;
- o any change to concomitant AD symptomatic medications during the study.

The estimate of this analysis reflects the treatment effect of aducanumab if the drug is taken as directed.

4.3.2.3.2 Per-protocol analysis

The per-protocol analysis will be done using the same model as the primary analysis (Section 4.3.2.1) and applying in the per-protocol population (Section 4.1.1).

4.3.2.3.3 Responder analysis

To further assess whether subjects on aducanumab progress differently from those on placebo, responder analysis will be conducted. The responders will be determined by a threshold of the primary endpoint, i.e., subjects whose change from baseline CDR-SB at Week 78 is smaller than or equal to the threshold will be classified as responders and otherwise will be classified as non-responders. All subjects with missing data at Week 78 will be classified as non-responders.

The responder analysis will be conducted for two threshold values: 0.5 or 1.5, i.e., subjects whose change from baseline CDR-SB at Week $78 \le 0.5$ or ≤ 1.5 . The number of responders

Final V1.0

and the response rate will be summarized by treatment group. The dichotomized response, responder vs. non-responder, will be modeled using a logistic regression with the following covariates: treatment group, baseline CDR-SB, baseline MMSE, AD symptomatic medication use at baseline (yes/no), region, and laboratoy ApoE £4 status (carrier/non-carrier). In addition to the two selected threshold values, the continuous responder curve that displays the percentage of responders under a wide range of threshold values will be presented by treatment group.

Since all missing data will be considered as non-response, which is a special form of missingnot-at-random, this analysis can provide additional insights for the robustness of the primary analysis results.

4.3.2.3.4 Slope analysis

Slope analysis will be conducted to assess the difference between each aducanumab treatment group and placebo in the slope of change from baseline in CDR-SB up to Week 78. A reduction in the slope of the aducanumab treatment group compared with placebo would indicate a slower rate of disease progression, thus reflecting a disease modifying effect of aducanumab. An MMRM model will be used, with dependent variable as the change from baseline CDR-SB score at each visit and with fixed effects of treatment group, time (as a continuous variable), treatment group-by-time interaction, baseline CDR-SB, baseline CDR-SB by time, baseline MMSE, AD symptomatic medication use at baseline (yes/no), region, and laboratory ApoE &4 status (carrier/non-carrier). The continuous time variable is calculated as number of years since the 1st infusion, so the slope estimate reflects the annual rate of change. The same methods as in the primary analysis will be considered for the covariance structure and the degrees of freedom.

4.3.2.3.5 Divergence effect analysis

A divergence effect analysis will be performed to assess whether the treatment difference between the aducanumab treated patients and the placebo patients increases over time [Li 2017]. A linear trend test will be conducted on treatment difference at Week 26, 50 and 78 estimated from the MMRM model of Section 4.3.2.1, to assess if the slope of the treatment difference is positive or not. Let the estimate of treatment difference be δ_i at time point t_i , where $t_i = 26$, 50 and 78 (week). The least-square estimate of the slope is

$$\beta_{DIF} = \frac{\sum (t_i - \bar{t})\delta_i}{\sum (t_i - \bar{t})^2},$$

where \bar{t} is the mean of t_i 's. The hypothesis to be tested is

$$H_0: \beta_{DIF} \leq 0$$
 versus $H_a: \beta_{DIF} > 0$.

Given β_{DIF} is a linear combination of the treatment difference δ_i , this analysis can be implemented by the "estimate" statement in the SAS proc mixed procedure.

4.3.2.4 CDR subscores and CDR global score

The CDR is comprised of 6 domains: Memory, Orientation, Judgment and Problem Solving, Community Affairs, Home and Hobbies, and Personal Care. CDR-SB is the sum of the scores

Final V1.0

for these 6 domains. In addition, two CDR subscores have been proposed [Tractenberg 2005]: a "cognitive" subscore equaling the sum of the Memory, Orientation, and Judgment and Problem Solving box scores, and a "functional" subscore equaling the sum of Community Affairs, Home and Hobbies and Personal Care box scores. For each of the 6 box scores, and the CDR cognitive subscore and CDR functional subscore, the baseline value and the change from baseline at each post-baseline visit will be summarized by treatment group. The same MMRM model as the primary analysis will also be applied to the CDR cognitive subscore and CDR functional subscore.

The CDR global score is a composite score obtained by combining the 6 box scores using a scoring algorithm that weights memory as the primary domain and all other domains as secondary [Morris 1993]. The distribution of CDR global score will be summarized (as a categorical variable) by treatment group at each post-baseline visit.

4.3.3 Secondary Efficacy Endpoints

4.3.3.1 Primary analysis of MMSE

The change from baseline MMSE scores will be summarized by treatment group at each post-baseline visit. An MMRM model will be used as the primary analysis to analyze change from baseline MMSE using fixed effects of treatment group, time (categorical), treatment group-by-time interaction, baseline MMSE value, baseline MMSE by time interaction, AD symptomatic medication use at baseline (yes/no), region, and laboratory ApoE &4 status (carrier/non-carrier). The same methods as in the primary analysis will be considered for the covariance structure and the degrees of freedom.

4.3.3.2 Primary analysis of ADAS-Cog 13

The change from baseline ADAS-Cog 13 scores will be summarized by treatment group at each post-baseline visit. An MMRM model will be used as the primary analysis to analyze change from baseline ADAS-Cog 13 using fixed effects of treatment group, time (categorical), treatment group-by-time interaction, baseline ADAS-Cog 13, baseline ADAS-Cog 13 by time interaction, baseline MMSE, AD symptomatic medication use at baseline (yes/no), region, and laboratory ApoE \$\partial \text{status}\$ (carrier/non-carrier). The same methods as in the primary analysis will be considered for the covariance structure and the degrees of freedom.

4.3.3.3 Primary analysis of ADCS-ADL-MCI

The change from baseline ADCS-ADL-MCI scores will be summarized by treatment group at each post-baseline visit. An MMRM model will be used as the primary analysis to analyze change from baseline ADCS-ADL-MCI using fixed effects of treatment group, time (categorical), treatment group-by-time interaction, baseline ADCS-ADL-MCI, baseline ADCS-ADL-MCI by time interaction, baseline MMSE, AD symptomatic medication use at baseline (yes/no), region, and laboratory ApoE & status (carrier/non-carrier). The same methods as in the primary analysis will be considered for the covariance structure and the degrees of freedom.

Final V1.0

The primary analysis of ADCS-ADL-MCI will use the pooled data from both Studies 221AD301 and 221AD302 (analysis for each individual study will also be performed). Pooled data will be used for the primary analysis because functional outcomes are expected to be less sensitive to change within the study duration than cognition measures due to ceiling effects [Rockwood 2007], as subjects entering the study will have no or little measurable impairment at baseline. It has also been observed in previous studies of more impaired patients (mild to moderate/severe) that functional outcome treatment effect sizes are small [Hansen 2007].

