1.2 Secondary Objectives and Endpoints

The secondary objectives of this study are:

- To assess the effect of monthly doses of aducanumab as compared with placebo on clinical progression as measured by the Mini-Mental State Examination (MMSE).
- To assess the effect of monthly doses of aducanumab as compared with placebo on clinical progression as measured by Alzheimer's Disease Assessment Scale-Cognitive Subscales (13 items) [ADAS-Cog 13].
- To assess the effect of monthly doses of aducanumab as compared with placebo on clinical progression as measured by Alzheimer's Disease Cooperative Study-Activities of Daily Living Inventory (Mild Cognitive Impairment version) [ADCS-ADL-MCI].

The secondary endpoints are:

- o Change from baseline in MMSE score at Week 78.
- o Change from baseline in ADAS-Cog 13 score at Week 78.
- o Change from baseline in ADCS-ADL-MCI score at Week 78.

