4 STATISTICAL ANALYSIS METHODS

4.1 General Considerations

This statistical analysis plan (SAP) only covers the analyses for the primary, secondary and tertiary objectives for the placebo-controlled portion of the study. Hereafter, the placebo-controlled portion of the study will be referred to as "the study" in the rest of this SAP (e.g.,

Final V1.0

completion of the study means completion of the placebo-controlled portion). A separate SAP will be prepared for the analyses of the LTE period and integrated analyses across both portions of the study. The analyses of additional exploratory endpoints will be documented separately.

Summary tables will be presented using descriptive summary statistics. For continuous variables, summary statistics will generally include: number of subjects with data, mean, standard deviation, median, 25% percentile, 75% percentile, minimum and maximum. For categorical variables, this will generally include: number of subjects randomized or dosed, number with data, and the percent of those with data in each category.

There are two types of analysis displays for tables: by treatment group (analysis display A in Appendix 6.1) and by treatment group stratified by ApoE status (analysis display B in Appendix 6.1; here ApoE status refers to the status recorded in IXRS [see Table 1 for correspondence between treatment groups and treatment groups stratified by ApoE status]). The analysis display for each analysis will be defined in each section. All the listings will be presented by treatment group stratified by ApoE status, unless otherwise specified.

Unless otherwise specified, baseline value is defined as the most recent non-missing measurement collected prior to the first dose. Change from baseline will be defined as post-baseline value minus baseline value.

Unless stated otherwise, all statistical tests will be 2-sided with statistical significance level of 0.05.

The statistical software, SAS® will be used for all summaries and analyses.

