The same imputation algorithm will be applied to CDR-SB and MMSE, if only 1 box (of 6) of CDR is missing or if only 2 or fewer items (out of 11) are missing for MMSE. If the score from more than 1 box of CDR or more than 2 items of MMSE is not available, the CDR-SB or MMSE at that visit will be considered missing.

The total score of the tertiary endpoint NPI-10 will be imputed using the same prorating principle if only 1 item (out of 10) is missing. For EQ-5D and mPDQ-20, if any item is missing, any total or sum involving that item will be considered missing.

Considerations for multiple comparison adjustments

A sequential (closed) testing procedure will be used to control the overall Type I error rate due to multiple comparisons for the primary endpoint. The order of treatment comparisons is as follows: aducanumab high-dose versus placebo and aducanumab low-dose versus placebo. All comparisons after the initial comparison with p > 0.05 will not be considered statistically significant.

Secondary endpoints have been rank prioritized, in the order shown in Section 1.2. In order to control for a Type I error for the secondary endpoints, a sequential closed testing procedure will be used and will include both the order of the secondary endpoints and treatment comparisons. Specifically, for each of the secondary endpoints, a sequential (closed) testing procedure, as for the primary endpoint, will be used to control the overall Type I error rate due to multiple treatment comparisons. If statistical significance is not achieved for 1 or 2 treatment comparisons, all endpoint(s) of a lower rank will not be considered statistically significant for that 1 or 2 treatment comparisons, respectively.

There will be no multiple comparison adjustments for the sensitivity and supplementary analyses for the primary and secondary efficacy endpoints, the tertiary efficacy endpoints, the subgroup analyses or the additional analyses.

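### ADCS-ADL-MCI, third in this study's error-controlled sequence, is tested on data pooled with 221AD302 and no study term, so a significant result supports a pooled claim, not a 221AD301 claim

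*SAP*

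**What the plan says.** Section 1.2 lists three secondary endpoints for this study. The third is "Change from baseline in ADCS-ADL-MCI score at Week 78". Section 4.3.1 states "Secondary endpoints have been rank prioritized, in the order shown in Section 1.2", and to control Type I error "a sequential closed testing procedure will be used and will include both the order of the secondary endpoints and treatment comparisons". Section 4.1 sets the level: "all statistical tests will be 2-sided with statistical significance level of 0.05".

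Sections 4.3.3.1 and 4.3.3.2 analyse MMSE and ADAS-Cog 13 without any mention of pooling. Section 4.3.3.3 differs: "The primary analysis of ADCS-ADL-MCI will use the pooled data from both Studies 221AD301 and 221AD302". It adds in brackets that "analysis for each individual study will also be performed". The reason given is that functional measures are expected to be less sensitive over the study's duration, because of ceiling effects and the small effects seen earlier in more impaired patients.

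The MMRM in Section 4.3.3.3 has treatment, time, treatment-by-time and baseline score, followed by "baseline ADCS-ADL-MCI by time interaction, baseline MMSE, AD symptomatic medication use at baseline (yes/no), region, and laboratory ApoE" status. Study is not among the terms. Table 2 in Section 4.3.1 gives the analysis population for this endpoint as ITT and does not mention the second trial. Section 4.3.1 does not say how the testing sequences of the two trials relate once they meet at a pooled endpoint.

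**The concern.** On the natural reading, steps one and two of the secondary sequence use 221AD301 data and step three uses data from two trials. The objective in Section 1.2 belongs to this study, but the p-value that settles it does not. A significant result could come mainly or wholly from 221AD302 and still appear as the last success in the 221AD301 sequence.

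Two gaps make this harder to handle at reporting. First, nothing says what the pooled result means if the earlier steps are passed in one trial and fail in the other. Second, the listed model neither adjusts for study nor examines whether the treatment effect differs between studies, so it does not show where the effect comes from. Randomisation was carried out within each study, and an analysis of combined data would ordinarily respect that.

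**Working it through.** **The plan's own figure.** The SAP gives no power for ADCS-ADL-MCI. Its only power statement (Section 3) is for CDR-SB: 450 per group, difference 0.5, SD 1.92, 30% drop-out, about 90% power. This reproduces. The formula needs 310 evaluable per group, and 310 / 0.70 = 443. With 450 × 0.70 = 315 evaluable, power is 90.5%. The figure does not carry over to ADCS-ADL-MCI, so power for that endpoint is treated below as an assumption with a range.

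**Inputs.** Two-sided level 0.05, critical value 1.960 (Section 4.1). 1:1:1 allocation (Section 2.1). 221AD302 is described as identically designed (Section 3). Equal size and equal SD in the two trials are assumed. All probabilities are for one dose comparison, given that the earlier steps in 221AD301 have been passed.

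**Pooled test.** With equal trials, pooled Z = (Z301 + Z302) / √2.

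*No effect in either trial.* Pooled Z is standard normal. The test rejects with probability 5% two-sided, 2.5% in favour of drug. The pooled hypothesis is tested at its stated level.

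*No effect in 221AD301, an effect in 221AD302.* If 221AD302 alone has power p, its expected Z is 1.960 + z(p). The expected pooled Z is that value / √2, and P(pooled test favours drug) = Φ(expected pooled Z − 1.960).

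| Assumed power of 221AD302 alone | Expected Z302 | Expected pooled Z | P(pooled test favours drug) |
|---|---|---|---|
| 30% | 1.436 | 1.015 | 17% |
| 50% | 1.960 | 1.386 | 28% |
| 80% | 2.802 | 1.981 | 51% |
| 90% | 3.242 | 2.292 | 63% |
| 95% | 3.605 | 2.549 | 72% |

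A test on 221AD301 data alone would favour drug in 2.5% of cases in every row.

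*Observed values.* The pooled test reaches 1.960 when Z301 + Z302 = 1.960 × √2 = 2.772. If Z302 = 3.0, then Z301 = −0.23 is enough.

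**Missing study term.** Let the mean change differ by d SD between two equal-sized studies. Leaving study out adds d²/4 to the residual variance, so the standard error grows by √(1 + d²/4). For d = 0.1 this is 1.0012 (0.1%), and for d = 0.5 it is 1.0308 (3.1%). Bias arises only if the arms have different shares of the two studies: a 5-point difference in share with d = 0.3 gives 0.05 × 0.3 = 0.015 SD. All these values of d and of the share difference are assumptions.

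**What pooling buys.** If both trials have the same true effect, pooled power is Φ(√2 × (1.960 + z(p)) − 1.960). Single-trial power of 30%, 50% or 80% becomes 53%, 79% or 98%.

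**The case against.** The pooling is stated openly and reasoned, and the single-study analyses are planned, so a reader of the results could see whether 221AD302 drives the finding. Type I error is controlled for the hypothesis that the SAP chose to test. Nothing in the SAP says that the pooled result will be credited to 221AD301 alone. CDR-SB, MMSE and ADAS-Cog 13 are not pooled, so replication is kept for them. The power gain is real where an effect exists. All of this stands, and it is why the pooled test need not leave the sequence.

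The 63% row should not be read as the expected case. It needs 221AD301 to succeed on the earlier endpoints with no functional effect at all, while an identically designed trial has 90% power on a measure that the SAP itself calls less sensitive. The lower rows may be nearer the mark, but the documents do not settle which applies.

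A reader might infer that both trials will report one and the same p-value, so that a double success is one result counted twice. The 221AD302 SAP is not shown, and an identical design does not establish an identical testing rule. If that SAP does use the same rule, then with the earlier steps passed in both trials and no effect on this endpoint, both would be falsely significant together 5% of the time, against 0.05 × 0.05 = 0.25% for separate tests. That 5% is conditional: if MMSE were also null in both trials, passing that step in both would itself have probability of at most 0.25%.

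It can also be said that the model paragraph in Section 4.3.3.3 follows the single-study template and that pooling is added only afterwards. That may explain the omission, but no other model is given for the pooled data.

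**Conclusion.** The point holds in a limited form. The third-ranked secondary endpoint of this study has a primary analysis on two trials, with a listed model that omits study. A significant pooled result is valid evidence for a pooled effect at the 5% level. It does not control error for a claim specific to 221AD301: under the assumptions above, the chance of a pooled success when 221AD301 has no effect ranges from 17% to 72%, depending on the power assumed for 221AD302.

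The omitted study term is a small matter for precision and bias. Its weight lies in leaving differences between the trials unexamined. The documents do not support saying that the plan inflates Type I error for the hypothesis it names. The main gap is one of rules: the SAP does not say what claim the pooled p-value supports, or how the two trials' sequences combine to permit that claim.

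**What to change.** 1. In Section 4.3.3.3, add study and study-by-time as fixed effects to the pooled model, and report the treatment-by-study interaction with the estimate for each study. This needs no new data; the expected precision gain is small.
2. In Sections 4.3.1 (text and Table 2) and 4.3.3.3, state that the pooled p-value supports only a pooled claim, and set out which earlier steps must be passed, and in which trial or trials, before it may be tested. Show in Table 2 that the data are pooled.
3. Require the already planned 221AD301-only estimate, with its confidence interval, to be shown beside the pooled result before any statement is made about ADCS-ADL-MCI in 221AD301.

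These three changes cost SAP wording only. A further option for the sponsor is to put the 221AD301-only test in this study's sequence and report the pooled analysis as supportive. That gives study-specific inference but gives up power, for example 50% instead of 79% if the two trials share the same effect, so it is a choice rather than a correction.
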